1. Adults between 18 and 50 years with rotator cuff tendinopathy.

Selection criteria

Inclusion criteria

1. Adults between 18 and 50 years old with rotator cuff tendinopathy defined as clinically compatible and confirmed by ultrasound.
2. At least 3 months of failed conservative treatment (decreased activity, anti-inflammatories, kinesiology for at least 3 months before diagnosis).

Exclusion criteria

1. Refusal to participate or informed consent,
2. previous shoulder surgery,
3. Partial or total tears of the rotator cuff,
4. Patients with shoulder osteoarthritis > 2 according to the Samilson and Prieto classification
5. Advanced fatty infiltration of the rotator cuff muscles (STAGE 3 or 4 according to Goutallier)³²
6. Systemic or rheumatoid arthritis,
7. uncontrolled diabetes,
8. Acute or chronic infections of the shoulder to be operated on
9. Ongoing cancer chemotherapy therapies
10. Sepsis, septic arthritis, osteomyelitis or other ongoing infectious processes;
11. Patients with autoimmune diseases;
12. pregnant,

Eligible patients will be enrolled in the study by giving their informed consent.

Preparation of platelet-rich plasma

For the PRP group, a leukocyte-poor preparation from a prepackaged kit (RegenLab, Lausanne, Switzerland) will be used. According to the manufacturer's manual, 10 ml of venous blood will be drawn into a blood collection tube containing a sodium citrate anticoagulant and a proprietary separating gel (thixotropic gel) to isolate the red and white blood cells from the PRP. Samples will be centrifuged at 1500g for 5 minutes to produce approximately 7 mL of 80% platelets at 1.6x concentration. The manufacturer reports a filtration of 99.7%, 87 to 89%, 70 to 75%, and 96.5% of red blood cells, white blood cells, mononuclear cells, and granulocytes, respectively. The supernatant is then resuspended by inverting the tube several times and withdrawn into a separate 5 mL syringe for subacromial injection.

This procedure will be performed 2 times in each patient. The product from the first kit will be injected into the patient. Instead, the product from the second kit will be used to evaluate the final composition of the PRP. These specific measurements will include: the final average of platelets, leukocytes and erythrocytes, and the specific formula of leukocytes and growth factors. This will allow us to establish a correlation between the specific composition of the PRP and the functional results of the patient.

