Variables to be measured and data documentation

All the variables to be measured will be recorded in a RedCap database specially designed for this clinical trial.

A) Demographic and related to the injury.

They will be recorded by the principal investigator 24-48 hours prior to the infiltration.

- Sex: male - female
- Age: Age in years on the day of infiltration
- Smoking: yes-no

B) Cynic variables

Pre-infiltration evaluation: It will be in charge of the principal investigator and it will be carried out 24-48 hours before the infiltration in the orthopedics office.

In it will be evaluated:

clinical variables: Mobility - Pain - Functional Scores (ASES - Constant) - Sleep disorders (Pittsburgh Score)

Imaging variables: Chronic tendinopathy will be defined as the presence of a hyperintense signal in the supraspinatus on magnetic resonance imaging (carried out a maximum of 6 months prior to clinical diagnosis), with the absence of partial or total ruptures of the tendon or as the presence of a hyperechoic signal in the supraspinatus. supraspinatus with increased intratendon Doppler flow. The presence of the tendinopathy will be confirmed by ultrasound the week prior to the infiltration to rule out the progression of the tendinopathy to a partial rupture of the tendon and to evaluate the presence of flow within the supraspinatus as a sign of tendinopathy with echodoppler.

Post-infiltration evaluation:

In it will be evaluated:

clinical variables: Mobility - Pain - Functional Scores (ASES - Constant) - (Pittsburgh Score) at one month, 3 months and 6 months postinfiltration. It will be in charge of the Shoulder Fellow who will not know to which branch of treatment the patient was assigned. That is to say it will be *blinded to intervention*.

Imaging variables: The presence of vascular flow within the tendon will be measured in the musculoskeletal ultrasound 6 months after the infiltration in the usual way. It will be in charge of a doctor specialized in musculoskeletal ultrasound who does not will know to which treatment arm the patient was assigned. That is to say it will *beblinded to intervention*.

The variables that will be evaluated are described below:

- Mobility: *The 4 mobility parameters will be measured in degrees with a goniometer*
 - Anterior flexion
 - Abduction
 - External Rotation with the arm at 90⁰of abduction
 - Internal Rotation with the arm at 90⁰of abduction

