- Pain: The visual analogue scale (VAS) will be used to assess the level of pain during activities of daily living. 0 will be considered as "absence of pain" and 10 as "the worst pain of your life".
- General function of the shoulder: The ASES (American Shoulder and Elbow Surgeons) score will be used.¹⁵ (*Annex 2*) and Constant's score¹⁶ (*Annex 3*) Both scores evaluate the general functionality of the shoulder in different activities of daily living, the global mobility of the shoulder, and pain with usual tasks. They are scores ranging from 0 to 100. Both scores are validated and are the reference scores for clinical research on rotator cuff pathology.^{15,16}
- Sleep disorders: The Pittsburgh score will be used.²⁰ (*Annex 4*)

c) Imaging variables

- Magnetic resonance imaging (MRI) of the affected shoulder:

The preinfiltration MRI will measure the presence of pathological hyperintensity in the supraspinatus, in the absence of partial or total tears of the rotator cuff.

The resonance must have been performed a maximum of 6 months prior to the clinical diagnosis of the tendinopathy. Otherwise it will be repeated.

Ultrasound 1 week before infiltration and 6 months after infiltration:

The shoulder musculoskeletal ultrasound that will be performed on all patients 1 week before infiltration will confirm the diagnosis of cuff tendinopathy and the absence of partial or total cuff tears. In addition, an echodoppler will be performed to determine the presence of intratendinous flow as a manifestation of tendinopathy. In the post-infiltration control musculoskeletal ultrasound 3 months after the infiltration, tendon healing will be evaluated, which will be defined as the absence of intratendinous vascular flow. Both MRI and ultrasound are part of the study and routine follow-up of patients treated for rotator cuff tendinopathy.

d) Variables related to security

Adverse effects and immediate post-infiltration complications, one month, 3 months and 6 months post-infiltration will be recorded.

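### Follow-up tendon healing is defined by absent Doppler flow alone, so a newly torn tendon without flow would count as healed, and new tears are not a prespecified outcome

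*Combined protocol and SAP*

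**What the plan says.** Before infiltration, the ultrasound has two tasks. Under B), in the imaging paragraph of the pre-infiltration evaluation, it is done "to rule out the progression of the tendinopathy to a partial rupture of the tendon", and also to look for flow inside the supraspinatus. Section c) Imaging variables repeats this: the scan "will confirm the diagnosis of cuff tendinopathy and the absence of partial or total cuff tears", and a Doppler reading for flow is then added. Tears also bar entry; the exclusion criteria list "Partial or total tears of the rotator cuff".

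After infiltration, only one of the two tasks is named. Under Post-infiltration evaluation: "The presence of vascular flow within the tendon will be measured in the musculoskeletal ultrasound 6 months after the infiltration in the usual way". The reader is a blinded specialist in musculoskeletal ultrasound. Section c) then gives the response rule: "tendon healing will be evaluated, which will be defined as the absence of intratendinous vascular flow". The evaluation scheme lists only a musculoskeletal Doppler ultrasound at follow-up.

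For safety, section d) states: "Adverse effects and immediate post-infiltration complications, one month, 3 months and 6 months post-infiltration will be recorded". It names no particular event.

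**The concern.** The plan recognises that tendinopathy can progress to a tear, looks for this just before injection, and excludes patients who have it. The response rule at follow-up has no branch for the same event. A site applying the rule as written would put a torn tendon without flow in the best category.

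Two things are at stake. The healing proportion, which is the only structural measure after treatment, can count a poor structural result as a success. And a structural harm of either injection has no defined place in the data, although one secondary objective is to confirm the safety of PRP through systematic recording of adverse effects and complications.

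**Working it through.** **1. What is assessed, and when**

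| Place in the protocol | Tendon integrity | Doppler flow |
|---|---|---|
| Exclusion criteria | Yes, tears exclude | Not mentioned |
| B) Pre-infiltration imaging | Yes | Yes |
| c) Ultrasound 1 week before infiltration | Yes | Yes |
| Post-infiltration evaluation, imaging | Not named | Yes |
| c) Follow-up ultrasound | Not named | Yes, and it alone defines healing |
| d) Safety variables | Not named | Not named |

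The plan therefore treats integrity and flow as separate findings. Nor does it equate absence of flow with a normal tendon. Chronic tendinopathy can be established by a hyperintense MRI signal "with the absence of partial or total ruptures of the tendon or as the presence of a hyperechoic signal in the supraspinatus" with increased flow; the flow condition belongs to the second route, not to the MRI route.

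**2. The rule applied to the four possible follow-up results**

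| Tendon | Flow | Coded under the stated rule |
|---|---|---|
| Intact | Absent | Healed |
| Intact | Present | Not healed |
| New tear | Present | Not healed |
| New tear | Absent | Healed |

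The fourth row is the fault. It follows from the wording and needs no outside fact.

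**3. Size, under stated assumptions**

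The plan gives no figure for healing, tears or flow at follow-up. The one figure borrowed here is the number evaluable per arm: 50 × (1 − 0.10) = 45, as in Sample size. That 45 reproduces from the plan's own inputs (difference 1.5, SD 2.41, 90% power) with a one-sided 5% alpha: 2 × (1.645 + 1.282)² × 2.41² / 1.5² = 44.2, rounded up to 45. A two-sided alpha gives 55. That is a separate matter; here 45 serves only as a denominator.

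Let f be the share of intact tendons without flow, t the new-tear rate, and q the share of torn tendons without flow.

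- Healing as defined: (1 − t)f + tq
- Healing with an integrity condition: (1 − t)f
- Overstatement: tq, whatever the value of f

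Example with assumed f = 0.60, t = 0.05, q = 0.50: 0.595 against 0.570, an overstatement of 2.5 points.

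Overstatement in percentage points, with patients per arm (45 × t × q) in brackets:

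| t | q = 25% | q = 50% | q = 75% | q = 100% |
|---|---|---|---|---|
| 2% | 0.5 (0.2) | 1.0 (0.5) | 1.5 (0.7) | 2.0 (0.9) |
| 5% | 1.25 (0.6) | 2.5 (1.1) | 3.75 (1.7) | 5.0 (2.3) |
| 10% | 2.5 (1.1) | 5.0 (2.3) | 7.5 (3.4) | 10.0 (4.5) |

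**4. Effect on the comparison of arms**

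The distortion of the difference between arms is t₁q₁ − t₂q₂. It is zero if the products are equal. Within the grid it could lie anywhere from −9.5 to +9.5 points (10.0 − 0.5). The documents fix neither t nor q in either arm, so neither its sign nor its size is known.

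**The case against.** The strongest reply is that this variable is peripheral and that the gap may be harmless in practice. Four parts of that reply deserve an answer.

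- **Peripheral role.** The objectives cover VAS pain, ASES and Constant function, sleep and safety. Ultrasound healing is in none of them and does not drive the sample size. This stands, and it limits the severity.
- **Tears may still be seen and recorded.** A reader might infer that the follow-up scan is read for flow only and that tears would go uncounted. The text does not say that. The scan is a musculoskeletal ultrasound done in the customary way by a specialist, and the general complication category in section d) could hold a new tear. What remains is that no tear field is specified and no route is stated. The evaluation scheme places complications among the clinical variables, which the fellow collects, while the sonographer is responsible for the imaging variables. Capture is left to discretion.
- **Direction of bias.** A reader might infer that corticosteroid patients would tear more often, so that the rule inflates control healing and hides a benefit of PRP. The documents do not support this. The stated hypothesis concerns pain and function. The introduction says that corticosteroids do not reverse structural change and describes pro-regenerative effects of PRP in vitro; neither statement says that tears are more frequent after corticosteroid.
- **Few events.** Patients are 18 to 50 years old and are confirmed free of tears a week before injection. At an assumed 2% tear rate, fewer than one patient per arm is affected. This is fair, and it is why the size is given only as an assumed range.

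It can also be said that absence of flow is a consistent, if narrow, marker, because the plan uses flow as a sign of tendinopathy. That would defend a variable called absence of flow. It does not defend calling a torn tendon healed.

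**Conclusion.** The point holds as a faulty outcome definition and should be corrected. It is not a threat to the trial's main result. As written, the rule codes a newly torn tendon without flow as healed, and new tears are not prespecified as an outcome.

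If 2% to 10% of tendons tear and 25% to 100% of those lack flow, healing in an arm is overstated by about 0.5 to 10 percentage points, or 0.2 to 4.5 of 45 patients. All these rates are assumptions. No claim about which arm would gain is supported.

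The conclusion is independent of two neighbouring problems. The follow-up scan is placed at 3 months in the text of section c) and in the evaluation scheme, but at 6 months under Post-infiltration evaluation and in the heading within section c); these must be reconciled. Also, a patient who enters by the MRI route without flow could count as healed with no change. Resolving either would leave the fourth row of the second table as it is.

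**What to change.** Under Post-infiltration evaluation and in section c):

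- Define healing as no intratendinous flow and no partial or full-thickness tear on the follow-up ultrasound.
- Code any new partial or full-thickness tear as not healed (progression), whatever the flow.
- Have the blinded sonographer record tear status as none, partial or full at the scan already planned.

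In section d), state that new tears found on that scan are reported by arm as a structural safety outcome.

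The cost is one extra REDCap field and a few lines of wording, with no additional visit, scan or assessor. Healing proportions may come out slightly lower than under the present rule.

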4. Confirm that platelet-rich plasma is a procedure **safe** through the systematic recording of adverse effects and complications associated with its use.

Materials and methods

Design

Randomized controlled clinical trial, with intervention group and control group, usual treatment, blind for the treatment received by the patient and for clinical and radiological evaluation.

Scope

The entire study will be carried out at the Hospital Italiano de Buenos Aires headquarters.

Schedule - masking - intervention

Stage 1: All patients with rotator cuff tendinopathy, clinically diagnosed and confirmed by MRI, will be invited to participate in this study.

After confirming that the patient meets the inclusion criteria, the study will be explained in detail through the informed consent process (See Consent Annex 1).

Stage 2: Once the patient agrees to participate and has signed the informed consent, they will be randomized (see randomization).

To the patients of group **1:** (control) a subacromial infiltration with corticosteroids (betamethasone 2 mg) will be performed under ultrasound control.

To the patients of group **2:** (Intervention) a subacromial infiltration with PRP will be performed under ultrasound control.

The week prior to the infiltration, all patients will undergo a prior ultrasound to confirm rotator cuff tendinopathy and rule out associated supraspinatus ruptures.

Masking of patients:

At the time of blood collection, patients will be placed in a hemotherapy extraction chair with a screen that will prevent the patient from seeing their arm at the time of blood collection. All patients will have a local anesthetic (cutaneous lidocaine) placed in the crease of the elbow at the extraction site. The patients in the intervention group will be injected with the extraction needle and 20 ml of blood will be obtained for the preparation of the PRP.

On the other hand, the patients in the control group (corticosteroid) will be given anesthetic and a dermal micro-puncture will be performed with the vacutainer simulating blood extraction. After this, they will wait 1 minute, simulating the time it takes for the extraction bag to fill with 20 ml.

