In this way, we will ensure the masking of the treatment received, an essential condition in this type of study since the scores used and validated for the clinical evaluation of this pathology have a subjective component that could be altered or biased if the patient knows which treatment received. On the other hand, the control group, although it has active masking, only consists of a skin micropuncture with a previous local anesthetic, which does not present complications or adverse effects and may not be perceived by the patient due to the local anesthesia.

Both procedures will be carried out under antiseptic conditions by a Hemotherapy technician in the procedure room of the Hemotherapy Service.

Subsequently, the patients will be accompanied to the procedure room where the assigned treatment will be applied under ultrasound control by the principal investigator. For patients in the CS group, 1 vial of 2 ml of Betamethasone will be

applied. The injection will be performed through a posterolateral approach. The CS will infiltrate the subacromial bursa. For patients in the PRP group, a volume of 5 ml will also be injected through a posterolateral approach. Patients will be informed about possible adverse reactions to both injections. Patients will be allowed to continue activity as tolerated after the injection and each patient will receive a specific exercise program to do at home. Patients will not know what treatment they received, meaning they will be blinded to the intervention. For this, at the time of injection, the syringe will be covered with black insulating tape so that the patient cannot see the contents of the syringe.

stage 3: Once the intervention is finished, all the patients will be rehabilitated by the shoulder team of the rehabilitation center of the Italian Hospital of Buenos Aires. The rehabilitation protocol will be the one recommended by the American Shoulder and Elbow Society (ASES).²¹ which is commonly used in the hospital.

Stage 4: During the development of the rehabilitation protocol, the evolution of the patient will be objectively evaluated with the analogous visual scale, the ASES score, the Constant score and the Pittsburgh score. (*Annex 3 -4 and 5*) one month, 3 and 6 months post-infiltration. The physician in charge of the objective evaluation and documentation of the patient's scores will be the shoulder improvement fellow who will be blind to the intervention received by the patient.

Population

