In the event that the patient presents a complication, they will have the contact number of the principal investigator to be attended by him or by a surgeon from the team in the orthopedic clinics or on duty at the Italian Hospital of Buenos Aires. Likewise, the doctors on duty will be informed about the development of the following protocol in order to notify the principal investigator or a member of the team in the event that a patient presents any post-infiltration complication.

Scheme of the evaluation points in time, responsible for the evaluation and the variables that will be recorded

	pre-infiltration (24-48 hours prior)	1 month post-infiltration	3 months post-infiltration	6 months post-infiltration
Evaluator	Principal investigator	Shoulder Fellow	Shoulder Fellow (clinical variables) Sonographer (imaging variables)	Shoulder Fellow (clinical variables)
Variables Clinics	-Demographic -Mobility -Pain -Functional Scores (ASES – Constant - Pittsburgh)	-Mobility -Pain -Functional Scores (ASES – Constant-Pittsburgh) -complications	-Mobility -Pain -Functional Scores (ASES – Constant-Pittsburgh) -complications	-Mobility -Pain -Functional Scores (ASES – Constant-Pittsburgh) -complications
Imaging variables	Magnetic nuclear resonance Ecodoppler musculoesquelético		Ecodoppler musculoesquelético	

Statistical analysis raised

Quantitative variables will be presented as mean and standard deviation or median and interquartile interval according to the observed distribution. Categorical variables will be presented as proportions. The 95% confidence intervals will be calculated for each of the estimators.

The comparison of continuous data between two groups will be analyzed with the t test if the distribution of the variables is normal or with the Mann-Whitney-Wilcoxon test if it is not. The analysis of categorical data will be carried out with the chi-square test. Statistical analysis will be performed with STATA MP version 16 (Stata Corporation, College Station, TX). A p value less than 0.05 will be considered statistically significant.

Sample size

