To calculate the sample size, the expected values of the variable "pain" represented by the VAS, which is the main outcome variable, are used. The minimal clinically relevant difference (MCID) was previously described in the setting of rotator cuff disease as 1.5 points with a standard deviation of 2.41 points on a 10-point scale for shoulder pain.²² We will work with a type I error probability of 5% and a power of 90%. Using these parameters in a superiority formula, a sample size of 45 patients per group was calculated. Considering the possibility of a loss to follow-up of 10% of the patients per group, 50 patients per group will be included, with a total final sample of 100 patients. The sample size was calculated using the formula of Fleiss et al.²³

Randomization

All included patients will be randomized after obtaining informed consent. Each patient will be randomly assigned a treatment arm using the online randomizer (<http://protocolos.hospitalitaliano.org.ar>) to treatment arms 1 (control) or 2 (intervention)

ethical considerations

Participation in the study will be in all cases voluntary and certified by the informed consent process. The study will be carried out in full accordance with current national and international regulations: Declaration of Helsinki of the World Medical Association, Provision 6677/10 of ANMAT, and the Standards of Good Clinical Practices ICH E6.

The proposed intervention does not frequently present adverse events and there are known contraindications for its application. The procedure will be paid for by the financing of the study, it will not imply any cost to the patient or their health coverage. The costs of monitoring and periodic evaluations will be borne by the study investigators.

All study data will be treated with the utmost confidentiality, with restricted access only to authorized personnel for the purposes of the study in accordance with current legal regulations National Law on Protection of Personal Data 25,326 (Habeas Data Law).

Damage or complications

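### The plan does not say whether follow-up VAS or change from baseline is compared, and it names only unadjusted tests although baseline scores are already collected

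*Combined protocol and SAP*

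**What the plan says.** The section Statistical analysis raised gives one rule for all continuous outcomes: "The comparison of continuous data between two groups will be analyzed with the t test if the distribution of the variables is normal". For data judged not to be normal, the alternative is given as follows: "or with the Mann-Whitney-Wilcoxon test if it is not". On estimation, the section adds: "The 95% confidence intervals will be calculated for each of the estimators". It does not define the estimators. It contains no ANCOVA, regression or mixed model, and it does not name the variable or the visit to be compared.

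The Hypothesis and the primary objective speak of improvement in pain but define no change score. Sample size makes VAS the main outcome and uses a difference of 1.5 with an SD of 2.41. It does not say whether that SD belongs to a follow-up score or to a change.

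Baseline values are planned. The pre-infiltration evaluation covers "clinical variables: Mobility - Pain - Functional Scores (ASES - Constant) - Sleep disorders (Pittsburgh Score"), and the same variables are measured again at 1, 3 and 6 months. On who takes baseline, and when, the text says: "It will be in charge of the principal investigator and it will be carried out 24-48 hours before the infiltration".

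On the order of events, Stage 2 of the schedule says: "Once the patient agrees to participate and has signed the informed consent, they will be randomized". The Randomization section agrees: "All included patients will be randomized after obtaining informed consent". The masking section then says that "the assigned treatment will be applied under ultrasound control by the principal investigator".

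**The concern.** Two things are missing. First, the primary comparison is not fixed. Follow-up VAS and change in VAS are different analysis variables. With the same patients they can give different estimates, p values and power. Improvement in the hypothesis hints at change, but a lower follow-up score than control could be reported in the same words.

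Second, the plan leaves unused the baseline information that it pays to collect. Adjusting for baseline VAS would settle the choice, and would be about as precise as the better unadjusted test, or more so.

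Two related points bear on the remedy:

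- The fallback to Mann-Whitney changes what is estimated. That test does not estimate the mean difference of 1.5 on which the trial was sized. No type I error harm is claimed for the switch.
- Adjustment is safe only if baseline is recorded before allocation is known. The text places randomisation after consent and baseline 24-48 hours before injection, without ordering the two. The principal investigator takes baseline and, under the masking section, also injects. Blinding is stated expressly for the follow-up assessors but not for this one.

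**Working it through.** **Inputs from the documents (Sample size):** difference 1.5; SD 2.41; type I error 5%; power 90%; 45 per arm before and 50 after 10% loss. Sidedness is not stated.

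**Assumptions, not in the documents:** the correlation ρ between baseline and follow-up VAS, shown from 0.1 to 0.7; equal SDs at both times unless stated; 45 per arm analysed.

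**1. The plan's own figure.** n per arm = 2 × [(z_α + z_β) × 2.41 / 1.5]².

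- One-sided 5%: 2 × [(1.645 + 1.282) × 1.607]² = 44.2, so 45. This matches.
- Two-sided 5%: 2 × [(1.960 + 1.282) × 1.607]² = 54.2, so 55. This does not match.
- Loss: 45 / 0.90 = 50. This matches.

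For an unadjusted comparison, 45 is therefore a one-sided figure. Both sidednesses are carried below.

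**2. SD for each analysis if 2.41 is the SD of follow-up VAS.**

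- Follow-up t test: 2.41.
- Change-score t test: 2.41 × √(2(1−ρ)), which is 3.233, 2.852, 2.410 and 1.867 at ρ = 0.1, 0.3, 0.5 and 0.7.
- ANCOVA: 2.41 × √(1−ρ²), which is 2.398, 2.299, 2.087 and 1.721.

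Power is from the noncentral t distribution with noncentrality 1.5 / (SD × √(2/45)), on 88 df for the t tests and 87 for ANCOVA.

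| ρ | Follow-up, 2-sided | Change, 2-sided | ANCOVA, 2-sided | Follow-up, 1-sided | Change, 1-sided | ANCOVA, 1-sided |
|---|---|---|---|---|---|---|
| 0.1 | 83.1% | 58.6% | 83.5% | 90.1% | 70.5% | 90.3% |
| 0.3 | 83.1% | 69.4% | 86.4% | 90.1% | 79.7% | 92.3% |
| 0.5 | 83.1% | 83.1% | 92.1% | 90.1% | 90.1% | 95.9% |
| 0.7 | 83.1% | 96.5% | 98.3% | 90.1% | 98.4% | 99.3% |

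Half-widths of the 95% CI at ρ = 0.1, 0.3 and 0.5 are 1.01 throughout for follow-up; 1.35, 1.19 and 1.01 for change; and 1.00, 0.96 and 0.87 for ANCOVA.

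**3. If 2.41 is instead the SD of change.** The follow-up SD is 2.41 / √(2(1−ρ)) and the ANCOVA SD is 2.41 × √((1+ρ)/2).

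| ρ | Follow-up, 2-sided | Change, 2-sided | ANCOVA, 2-sided |
|---|---|---|---|
| 0.3 | 93.3% | 83.1% | 95.2% |
| 0.5 | 83.1% | 83.1% | 92.1% |
| 0.7 | 61.9% | 83.1% | 88.6% |

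One-sided, ANCOVA has 97.7%, 95.9% and 93.7%, against 90.1% for change. At ρ = 0.5 the two readings of 2.41 describe the same trial, so their agreement there is not independent support.

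**4. Unequal SDs, 2.41 as follow-up SD.** Only the change score is affected. Its two-sided power at ρ = 0.1, 0.3 and 0.5 is 69.0%, 79.1% and 90.0% if the baseline SD is 0.75 times the follow-up SD, and 48.4%, 58.3% and 72.2% if it is 1.25 times.

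**5. Simulation with the slope estimated** (40,000 runs per ρ; ρ = 0.1, 0.3, 0.5). ANCOVA power was 83.2%, 86.0% and 91.8% two-sided, close to the formula. Two-sided type I error was 5.0% to 5.2% for all three tests when baseline was clean.

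**6. Why baseline must come before allocation** (an illustration, not a claim about this trial). If baseline VAS were recorded 0.5 point higher in one arm, the null estimate would shift by 0 for follow-up, by 0.5 for change, and by ρ × 0.5 = 0.05, 0.15 or 0.25 for ANCOVA at ρ = 0.1, 0.3 or 0.5. Two-sided ANCOVA type I error would then be 5.1%, 6.1% or 8.4%.

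**The case against.** The strongest reply is that naming one outcome form and one visit would cure the ambiguity. On this view ANCOVA is an efficiency preference, since the unadjusted tests are valid. It is true that the ambiguity could be cured that way. But the choice between the two unadjusted tests needs ρ, which the plan does not have. Either can be clearly the worse one: change at ρ = 0.1 if 2.41 is the follow-up SD, follow-up at ρ = 0.7 if it is the SD of change. ANCOVA removes that gamble for about one degree of freedom.

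A second reply is that the gain depends on assumptions and can be small. This stands. With 2.41 as follow-up SD, the gain over the follow-up test is 0.4 points at ρ = 0.1, and the gain over change is under 2 points at ρ = 0.7. With 2.41 as the SD of change and ρ = 0.3, the gain over follow-up is about 2 points. A smaller baseline SD also helps the change score. No single power figure can be claimed. ANCOVA still has the highest power in every case tabulated.

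Third, 45 per arm is not uniquely a one-sided figure: a two-sided calculation that allowed for baseline adjustment at ρ of about 0.42 gives 54.25 × (1 − 0.42²) = 44.7, so 45. That is correct, but Sample size mentions no adjustment.

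Fourth, the Design section describes clinical evaluation as blind without limiting this to follow-up, VAS is the masked patient's own rating, and the section Damage or complications assigns the injections to an unspecified doctor of the shoulder team. All of this is in the text. None of it places baseline before allocation, and no contamination is alleged. The timing is a condition of the remedy.

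**Conclusion.** The concern holds. The documents do not say whether follow-up VAS or change is compared, and they name no analysis that uses the baseline scores. The consequence is an unfixed primary comparison and unused precision; the validity of a pre-fixed unadjusted test is not in question.

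With 2.41 as follow-up SD, equal SDs and 45 per arm, the gap between the two unadjusted options at two-sided 5% is 83.1 − 58.6 = 24.5 points in favour of follow-up at ρ = 0.1, nil at 0.5, and 96.5 − 83.1 = 13.4 points in favour of change at 0.7. The gain of ANCOVA over the follow-up test is negligible at ρ = 0.1. At ρ = 0.5 it is about 9 points two-sided and 6 points one-sided.

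The omission is certain from the text. The size of the loss rests on the assumed ρ, the SD ratio and the meaning of 2.41. The sponsor should make the change, although the trial is not invalid without it.

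**What to change.** Before unblinded data are seen:

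- Make ANCOVA of follow-up VAS at one named primary visit, with treatment and baseline VAS as terms, the single primary analysis. Report the adjusted mean difference with its 95% CI.
- State that baseline VAS and the other baseline scores are recorded before randomisation. If for some patients they were recorded after the assessor knew the allocation, add the unadjusted follow-up comparison as a sensitivity analysis.
- Use the same baseline-adjusted approach for ASES, Constant, Pittsburgh and mobility.
- Keep Mann-Whitney as a sensitivity analysis only.

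The cost is analysis wording and about one degree of freedom. Placing baseline before allocation is a matter of conduct as well as wording and may change the order of visits, but the assessment is already planned and no new measurement or patient is needed.
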